2. OBJECTIVES

Primary Objective:

The objective of this study proposal is to explore the posaconazole drug exposure during treatment in different stages of inflammation.

Secondary Objective(s):

The secondary objective is to develop a multiple linear regression model to describe the contribution of inflammation to the variability in posaconazole concentration. Subsequently, the relation between change in CRP and change in drug plasma concentration from this

study will be compared with the results of our earlier prospective voriconazole study [NCT02074462] based on matched patients.

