4. STUDY POPULATION

4.1 Population (base)

Patients that receive posaconazole for treatment or (secondary) prophylaxis of fungal infections

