4.2 Inclusion criteria

In order to be eligible to participate in this study, a subject must meet all of the following criteria:

-aged ≥ 18 yrs -receive posaconazole -written informed consent

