8.1.2 Secondary study parameters/endpoints (if applicable)

Develop a multiple linear regression model that describes the contribution of inflammation on posaconazole levels. Compare the relation between change in CRP

and change in drug plasma concentration from this study with the results of our earlier prospective voriconazole study [NCT02074462] based on matched patients drug plasma concentration from this study will be compared with the results of our earlier prospective voriconazole study [NCT02074462] based on matched patients.

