8.3 Study procedures

-Patients starting on posaconazole treatment will be evaluated for inclusion.

-After informed consent is obtained medical data will be collected from the medical chart and plasma samples from routine analysis will be obtained.

-Samples for posaconazole and inflammatory analysis will be collected 3-4 times weekly during treatment. Inflammatory markers like CRP will be determined by the department of Clinical Chemistry of the UMCG. Other inflammatory markers of IL-6, IL-8 and procalcitonin will not be determined, since these markers are not routinely measured. Posaconazole plasma concentrations (trough levels) will be measured with a validated and externally tested LC-MS/MS method of analysis [Alffenaar *et al* J Chrom B 2009].

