10.2 Longitudinal data analysis

The longitudinal data of the posaconazole concentration will be analyzed with a linear mixed model. A log transformation will be performed if the data are not normally distributed. A random additive effect will be selected for patients to address different concentrations between patients. A first-order autoregressive correlation between posaconazole trough concentrations over time will also be selected to correct for differences in intervals between observations. To investigate the effect of inflammation on posaconazole concentration, the Wald type III test will be conducted after correcting for gender, age, posaconazole dose and route of administration, liver enzymes (ALP, ALAT, ASAT, γ -GT and total bilirubin) and the use of interacting co-medication. The analysis will be performed using SAS 9.3 (SAS Institute Inc., Cary, NC, USA). A p value < 0,05 is considered statistically significant.

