11.2 Recruitment and consent

After treatment with posaconazole is started by the attending physician, he or she informs the patient or representative of the patient, if the patient is not capable of giving informed consent, according to article 6 paragraph 1c of the WMO about the study. The patient or representative is allowed 48 hours for consideration of participation to the study. Written informed consent is obtained from the patient or the representative by the research nurse, study physician or investigator. The patient information letter and the informed consent form are attached.

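### The mixed model in section 10.2 has no term for time on posaconazole and no steady-state rule, so a CRP trend during early accumulation would bias the CRP effect

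*Combined protocol and SAP*

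**What the plan says.** Section 10.2 fits a linear mixed model to serial posaconazole troughs, with a random patient effect and AR(1) residual correlation. The Wald type III test of inflammation is "conducted after correcting for gender, age, posaconazole dose and route of administration, liver enzymes" and interacting co-medication. Time appears only in the residual correlation.

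On who is sampled and when:

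- Section 8.3: "Patients starting on posaconazole treatment will be evaluated for inclusion", and "Samples for posaconazole and inflammatory analysis will be collected 3-4 times weekly during treatment". These are trough levels. No first sampling day is given.
- Section 11.2: consent is sought after treatment has started, and "The patient or representative is allowed 48 hours for consideration of participation to the study".
- Section 4.2 sets no minimum time on the drug; beyond age, the criteria are only "receive posaconazole -written informed consent". Patients already established on posaconazole may therefore also enter.
- Section 4.1: "Patients that receive posaconazole for treatment or (secondary) prophylaxis of fungal infections". Treatment and prophylaxis patients are mixed, so no common CRP course is implied.

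No section mentions steady state, a run-in or the exclusion of early troughs.

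**The concern.** A trough taken before steady state is low because the drug is still accumulating. Dose and route do not explain this, since the level rises while both stay constant. A random intercept moves a patient's whole curve up or down, and AR(1) describes dependence between residuals. Neither puts a shared rise into the mean.

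If CRP falls over the same days, high CRP goes with low concentrations for reasons unrelated to inflammation.

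The Wald test is the only test of inflammation that section 10 specifies. The secondary aim, "Develop a multiple linear regression model that describes the contribution of inflammation on posaconazole levels", and the matched comparison with the voriconazole study are not worked out there. Section 1 expects no influence of inflammation on posaconazole. A falling CRP would bias the estimate downward and could hide a true rise, so the error can favour the expected conclusion.

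**Working it through.** **The plan's own figure.** The only sample-size figure is 30 patients (section 4.4), justified by feasibility. No effect size, SD or power is given, so there is nothing to reproduce, and N is not in dispute.

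**Inputs from the plan.** 30 patients, 3-4 samples a week, random intercept plus AR(1), significance level 0.05.

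**Assumed inputs (not in the plan).**

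- Half-life 24 or 36 h; fraction of steady state present at once f0 = 0 or 0.5.
- A trough every 2 days to about day 14, analysed on the log scale.
- Concentration: between-patient SD 0.4, residual SD 0.25, lag correlation 0.4.
- Log CRP: between-patient SD 0.8, noise SD 0.5, lag correlation 0.4.
- CRP change 4-fold, either log-linear over 14 days or front-loaded with a 3-day time constant.

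**Step 1: how far from steady state.** Fraction reached = 1 - (1 - f0) x 0.5^(hours / half-life).

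| First sample | 24 h, f0 = 0 | 36 h, f0 = 0 | 24 h, f0 = 0.5 | 36 h, f0 = 0.5 |
|---|---|---|---|---|
| Day 2 | 1 - 0.5^2 = 0.75 | 1 - 0.5^1.33 = 0.60 | 0.875 | 0.80 |
| Day 4 | 1 - 0.5^4 = 0.94 | 1 - 0.5^2.67 = 0.84 | 0.97 | 0.92 |
| Day 6 | 1 - 0.5^6 = 0.98 | 1 - 0.5^4 = 0.94 | 0.99 | 0.97 |

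The missing mean term is ln(fraction reached). It matters on day 2, less on day 4, and hardly on day 6.

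**Step 2: sign.** The bias in the CRP slope has the sign of the within-patient covariance between log CRP and ln(fraction reached). The latter rises, so falling CRP gives negative bias, rising CRP positive bias, and no net trend no mean bias.

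**Step 3: size with no true effect.** REML fit with CRP, random intercept and AR(1), no time term; 1000 runs per cell. Ranges span the half-life and f0 values, and both trend shapes where both were run. The ratio is the spurious multiplicative change in concentration per 4-fold higher CRP.

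| CRP course | First sample | Ratio | False positives |
|---|---|---|---|
| Falls in half | day 2 | 0.944-0.979 | 8-21% |
| Falls in half | spread over days 2-5 | 0.962-0.991 | 6-13% |
| Falls in half | day 4 | 0.969-0.996 | 5-9% |
| Falls in half | day 6 | - | 5-7% |
| Falls in half; 33-50% of patients already established | day 2 | - | 7-16% |
| No trend, or thirds rising, falling and flat | - | - | 4-7% |
| Limiting case: falls in all | day 2 | 0.881-0.961 | 17-72% |
| Limiting case: falls in all | day 4 | 0.945-0.992 | 6-23% |

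With linear plus log time added, the ratio was 0.99-1.01 and false positives 3-8% throughout.

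**Step 4: do the other 10.2 covariates remove it?** With simulated age, gender, dose, route, co-medication and five liver tests (500 runs per cell), half falling gave 7-23% (day 2) and 3-11% (day 4). They can shrink the bias but did not remove it.

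**Step 5: masking.** True effect +10% per 4-fold higher CRP, half falling:

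| First sample | Estimate, no time term | Detected | Estimate, linear plus log time | Detected |
|---|---|---|---|---|
| Day 2 | +4% to +8% | 11-40% | +10% | 54-57% |
| Day 4 | +7% to +10% | 26-51% | +10% | 49-53% |

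**Step 6: cross-check under different assumptions.** Three weeks of data, a CRP fall shared by almost all patients with a 5-day time constant, residual SD 0.3, first sample day 3, f0 = 0. The bias per CRP doubling was -1.1%, -2.6% and -3.6% for half-lives of 20, 30 and 36 h. Squaring puts these on the 4-fold scale: 0.989^2 = 0.978, 0.974^2 = 0.949, 0.964^2 = 0.929. False positives were 9%, 22% and 36%. If 90% of steady state was reached at once (30 h), they were 6%. A categorical time term gave 3.7-6.0%, and restriction to samples from day 7 gave 5.2-7.0%. With a day-1 start and CRP moving in balanced directions there was no mean bias, but the test still rejected in 10% of runs.

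**The case against.** The strongest case against concerns weight, not fact. Bias requires samples before steady state, a net CRP trend in those same days, and limited rapid loading. The plan fixes none of these. Consent follows the start of treatment and study samples follow consent, so a day-1 sample is the least likely. At day 4 with half the patients falling, the uncorrected false-positive rate (5-9%) nearly coincides with the corrected one (3-8%), and the spurious effect is at most about 3%. Longer follow-up dilutes the bias: in a rerun for day 2 and half falling, the ratio moved from 0.939-0.978 at 14 days to 0.954-0.990 at 42 days. The primary aim is only to "explore the posaconazole drug exposure during treatment in different stages of inflammation".

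Most of this stands and sets the limits of the point. The all-falling rows are limits, not expectations. But the 48 hours are a maximum for deciding about consent and not an analysis rule, so day 2 remains possible. Longer follow-up did not reliably protect the test: rejection was 8-26% at 14 days and 6-39% at 42 days, because the standard error shrinks as well.

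One further objection improves the fix. Section 5 describes dose changes guided by measured levels, and section 6.5 allows intravenous or oral use. Each change can start a new approach to steady state, which days since start does not capture. Concentration-driven dosing was not simulated.

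**Conclusion.** The concern holds as a conditional one. The mean model omits time on drug, no steady-state rule exists, and early troughs can enter. If CRP has a net trend during accumulation, the CRP coefficient is biased in a known direction. In the moderate scenario (half the patients falling 4-fold) the bias is about 2-6% per 4-fold CRP with a first sample on day 2 and 0.4-3% on day 4. The coefficient is essentially unbiased if CRP has no net trend, and the bias is negligible if sampling starts near steady state.

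These figures are a sensitivity range on assumed half-life, loading, CRP course and variances, not an estimate for this study. Because the objective is exploratory, this is a worthwhile improvement and not a failure of confirmatory error control. It should be made because it is cheap and because, with falling CRP, the bias can support the expected finding of no influence.

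**What to change.** In section 10.2, pre-specify:

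1. **A flexible fixed effect for days since the start of posaconazole**, either linear plus log time or a natural spline with 3 df, with the CRP effect reported with and without it. A linear term alone is not enough: with a front-loaded CRP fall and a first sample on day 2 it still rejected in 6-9% of runs (half falling) or 7-23% (all falling), against 5-6% for linear plus log time and for the spline.
2. **A sensitivity analysis** limited to samples after an early period fixed in advance and taken on an unchanged dose and route.
3. **The day of each sample relative to the first dose**, including for patients already on the drug at consent, and relative to the last dose or route change.

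The cost is SAP wording and derived timing variables; section 6.8 already takes administration data from the chart. The time term uses two or three degrees of freedom. The standard error of the CRP effect (log ratio per 4-fold, day 2) is about unchanged if half the patients fall: 0.045 with the term against 0.043-0.051 without. It grows by up to about 20% if a 4-fold fall is shared by all (0.048 / 0.040 = 1.20) and about 40% for a shared 8-fold fall (0.048 / 0.034 = 1.41).

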10.3 Other study parameters

Not applicable

10.4 Interim analysis (if applicable)

Not applicable

11. ETHICAL CONSIDERATIONS

11.1 Regulation statement

The study will be conducted according to the principles of the Declaration of Helsinki. No approval by the local ethical committee will be required, in accordance with Dutch Law (Medical Research Involving Human Subjects Act) due to the nature of this study

11.2 Recruitment and consent

After treatment with posaconazole is started by the attending physician, he or she informs the patient or representative of the patient, if the patient is not capable of giving informed consent, according to article 6 paragraph 1c of the WMO about the study. The patient or representative is allowed 48 hours for consideration of participation to the study. Written informed consent is obtained from the patient or the representative by the research nurse, study physician or investigator. The patient information letter and the informed consent form are attached.

11.3 Objection by minors or incapacitated subjects (if applicable)

In case of impaired consciousness or sedation, the patient is not able to object. The representative of the patient, according to article 6 paragraph 1c of the WMO, is then asked for informed consent. The representative of the patient is the legal representative, or (if no legal representative has been appointed) the person authorized in writing by the subject to act on his or her behalf, or (if no such person is available) the subject's spouse,

registered partner or other companion in life, thereafter the subjects parents, thereafter the subjects adult children and thereafter the adult siblings of the subject.

11.4 Benefits and risks assessment, group relatedness

No risks are related to this study as neither investigational drug is administered or intervention or invasive is performed. No benefit is expected for the participants.

11.5 Compensation for injury

As there is no additional risk for participation in this study, the METC of the UMCG granted exemption from liability insurance (art. 4 lid 1 Besluit verplichte verzekering bij medischwetenschappelijk onderzoek met mensen).

11.6 Incentives (if applicable)

None

12. ADMINISTRATIVE ASPECTS, MONITORING AND PUBLICATION

12.1 Handling and storage of data and documents

Data and documents are handled confidentially. A subject identification code list is used to link the data to the subject. The key to the code is safeguarded by the investigator. The investigator and the project leader have access to the source data via a secured data folder. The handling of personal data meets the criteria of the dutch Personal Data Protection Act (Wbp).

12.2 Monitoring and Quality Assurance

Monitoring will be preformed by a QA officer of the department. Written informed consent, inclusion & exclusion criteria will be checked for every patient. Data collection will be checked for every 5th patient.

12.3 Amendments

Amendments are changes made to the research after a favourable opinion by the accredited METC has been given. All amendments will be notified to the METC that gave a favourable opinion.

12.4 Annual progress report

The sponsor/investigator will submit a summary of the progress of the trial to the accredited METC once a year. Information will be provided on the date of inclusion of the first subject, numbers of subjects included and numbers of subjects that have completed the trial, serious adverse events/ serious adverse reactions, other problems, and amendments.

12.5 End of study report

The investigator will notify the accredited METC of the end of the study within a period of 8 weeks. The end of the study is defined as the last patient's last visit.

In case the study is ended prematurely, the investigator will notify the accredited METC within 15 days, including the reasons for the premature termination. Within one year after the end of the study, the investigator/sponsor will submit a final study report with the results of the study, including any publications/abstracts of the study, to the accredited METC.

12.6 Public disclosure and publication policy

The results of the study will be published without any restrictions to its content.

13. STRUCTURED RISK ANALYSIS

Not applicable

